## 1 SYNOPSIS

Title: A Multicenter, Single Arm, Open-label Study to Investigate the Efficacy and Safety of Ravagalimab (ABBV-323) in Subjects with Moderate to Severe Ulcerative Colitis Who Failed Prior Therapy	
Background and Rationale:	
Ulcerative colitis (UC) is a chronic, relapsing inflammatory disease of the rectum and/or large intestine characterized by inflammation and ulceration of the mucosal and submucosal intestinal layers. Despite increasingly available therapies, currently approved UC therapies have limited efficacy and have a potential for significant safety events. Thus, a large unmet need continues to exist for the treatment of UC.
 
CD40 is a tumor necrosis factor (TNF) receptor family member that plays an important role in lymphocyte activation and antigen presenting cell (APC) function. CD40 expression on epithelium, leukocytes, and vascular endothelium is elevated in systemic inflammatory diseases (e.g., Crohn's disease [CD], UC, rheumatoid arthritis [RA], and systemic lupus erythematosus [SLE]). Ravagalimab is a proprietary monoclonal antibody (mAb) that is a potent CD40 antagonist with no evidence of agonist activity. Evidence from in vitro studies, preclinical models, and human disease suggests that CD40 signaling is important in the pathogenesis of UC and inhibition of CD40 mediated signaling may be a potential treatment for patients with UC.

Objective(s) and Endpoint(s):	
Objective: To explore the efficacy, safety, and tolerability of ravagalimab as treatment in subjects with moderately to severely active UC.
 
Primary Efficacy Endpoint:
 
The proportion of subjects with endoscopic improvement (Mayo endoscopic subscore of 0 or 1) at Week 8.

Investigator(s):	Multi-center.
Study Site(s):	Approximately 35 sites; countries such as, but not limited to Canada, France, Germany, Hungary, Italy, Netherlands, South Korea, Spain, United Kingdom, and United States.
Study Population and Number of Subjects to be Enrolled:	The study population consists of adults with moderate to severe UC who failed prior therapy. Up to approximately 40 subjects will be enrolled.
Investigational Plan:	
Study M15-722 is a Phase 2a, multicenter, single arm, open-label study to investigate the efficacy and safety of ravagalimab in subjects with moderate to severe UC who failed prior therapy. The study contains a 35-day screening period, 2 treatment periods, and an 84-day follow up period from the last dose of study drug. The induction period is an open-label (OL) 12-week treatment period to evaluate the efficacy, safety, tolerability, pharmacokinetics (PK) and receptor occupancy (RO) of ravagalimab for inducing endoscopic improvement at Week 8. Subjects who achieve clinical response per Partial Adapted Mayo score at Week 12 may continue into the maintenance period. The maintenance period is an OL 92-week treatment period to assess efficacy and safety for maintenance of response with ravagalimab. An internal data monitoring committee (DMC) will review safety at regular intervals.

Key Eligibility Criteria:	
 
Subjects must understand and personally voluntarily sign and date an informed consent, approved by an independent ethics committee (IEC)/institutional review board (IRB), prior to the initiation of any screening or study-specific procedures.
 
Adult male or female, between 18 and 75 years of age, inclusive, at time of the Baseline visit.
 
Diagnosis of UC for at least 3 months prior to Baseline. Appropriate documentation of biopsy results consistent with the diagnosis of UC in the assessment of the Investigator, must be available.
 
Subject meets the following disease activity criteria: Active UC with an Adapted Mayo score of 5 to 9 points and endoscopic subscore of 2 to 3 (confirmed by central review).
 
History of inadequate response, loss of response, or intolerance to one or more of the approved therapies: infliximab, adalimumab, golimumab, vedolizumab, ustekinumab and/or tofacitinib. Dose and duration requirements are specified in Section 5.1.
 

Study Drug and Duration of Treatment:	Ravagalimab (100 mg/mL) Induction Period: 
 
OL ravagalimab 600 mg intravenous (IV) Week 0; ravagalimab 300 mg subcutaneous (SC) Weeks 2, 4, 6, 8, and 10
 
 Maintenance Period: 
 
Open-label ravagalimab 300 mg SC every other week (eow) from Week 12 to Week 102
 

Date of Protocol Synopsis:	04 December 2020

## 2 INTRODUCTION

### 2.1 Background and Rationale

---

#### Why Is This Study Being Conducted

Ulcerative colitis (UC) is a chronic, relapsing inflammatory disease of the rectum and/or large intestine characterized by inflammation and ulceration of the mucosal and submucosal intestinal layers. The hallmark clinical symptoms include bloody diarrhea associated with rectal urgency and tenesmus. The clinical course is marked by exacerbation and remission. Extraintestinal complications include arthritis, erythema nodosum, pyoderma gangrenosum, uveitis, and primary sclerosing cholangitis. Conventional therapies for the induction of remission include 5-aminosalicylic acid (5-ASA) derivatives, corticosteroids and the immunomodulatory agent cyclosporine. 5-ASA derivatives as well as thiopurines are used for the maintenance of remission. The biological agents infliximab, adalimumab, golimumab, vedolizumab, and ustekinumab as well as the Janus kinase (JAK) inhibitor tofacitinib are indicated for the induction and maintenance of remission in subjects with moderate to severe UC. Despite increasingly available therapies, currently approved UC therapies have limited efficacy and have a potential for significant safety events. Thus, a large unmet need continues to exist for the treatment of UC.

CD40 is a tumor necrosis factor (TNF) receptor family member that plays an important role in lymphocyte activation and antigen presenting cell (APC) function. CD40 expression on epithelium, leukocytes, and vascular endothelium is elevated in systemic inflammatory diseases (e.g., Crohn's disease [CD], UC, rheumatoid arthritis [RA], and systemic lupus erythematosus [SLE]). Ravagalimab is a proprietary monoclonal antibody (mAb) that is a potent CD40 antagonist with no evidence of agonist activity.

Evidence from in vitro studies, preclinical models, and human disease suggests that CD40 signaling is important in the pathogenesis of UC and inhibition of CD40 mediated signaling may be a potential treatment for patients with UC. For further details, please see ravagalimab Investigator's Brochure.

#### Clinical Hypothesis

Ravagalimab is safe and well tolerated in subjects with moderate to severe UC and leads to endoscopic improvement at Week 8.

### 2.2 Benefits and Risks to Subjects

---

Despite the availability of various UC therapies, including biologic and small molecule therapies, many patients still do not respond adequately to these treatments, gradually lose response over time or discontinue treatment due to significant adverse events (AEs). Thus, there remains a large unmet medical need for additional therapeutic options in UC for patients with inadequate response or intolerance to available therapies. Based on pre-clinical, clinical, and translational evidence, ravagalimab could potentially demonstrate efficacy with a favorable safety profile in the treatment of patients with moderately to severely active UC who have failed or have intolerance to approved biologics and/or tofacitinib.

In the Phase 1 studies ravagalimab was safe and well tolerated with no serious or severe AEs observed in healthy adult subjects. The dose regimen in Study M15-722 will not exceed the doses evaluated in the Phase 1 studies.

As with any immune modulating agent, ravagalimab has the potential to impair immune function resulting in a potential risk of infection, including opportunistic infections. The role of ravagalimab in tumor immunity is not well established at this time, but an increased risk of cancer associated with ravagalimab treatment cannot be excluded. Though the completed Phase 1 studies did not suggest a potential for drug-induced liver injury (DILI) with ravagalimab, DILI is under constant surveillance by sponsors and regulators and any suspected event of DILI in this study requires timely detection, evaluation, and follow-up of laboratory parameters. Local reactions to intravenous (IV) infusions or subcutaneous (SC) administered biologic therapies are uncommon, and are usually limited to redness, swelling, or induration at injection site. In Phase 1 studies, 1 subject on ravagalimab each experienced injection site reaction and injection site pain. The aforementioned safety risks were taken into account with the establishment of the safety monitoring measures in the eligibility criteria for this study. Furthermore, an internal data monitoring committee (DMC) will monitor safety at regular intervals (Section 6.3).

Blood sampling, IV infusions, and subcutaneous SC injections can cause local bruising, inflammation, and pain. The preparation for endoscopy, and the endoscopy and biopsy procedure itself, although generally well tolerated, can be associated with diarrhea, abdominal pain, and in more severe cases, perforation, bleeding, effects from anesthetic medications, and infection.

In view of the coronavirus disease of 2019 (COVID-19) pandemic, the benefit-risk profile of various immunomodulatory therapies on COVID-19 is being evaluated. At this time, the effects of ravagalimab on the course of COVID-19 is not known.

The benefit-risk profile of ravagalimab is considered appropriate for an experimental therapy at this stage of clinical development in an especially refractory patient population.

Taken together, the data support further development of ravagalimab in Phase 2 for subjects with moderate to severe UC who have failed prior biologic therapy and/or tofacitinib. For further details, please see findings from completed studies, including safety data in the ravagalimab Investigator's Brochure.

## 3 STUDY OBJECTIVES AND ENDPOINTS

### 3.1 Objectives

---

To explore the efficacy, safety, and tolerability of ravagalimab as treatment in subjects with moderately to severely active UC.

## 3.2 Primary Efficacy Endpoint

---

The primary efficacy endpoint is the proportion of subjects with endoscopic improvement (Mayo endoscopic subscore of 0 or 1) at Week 8. Note that evidence of friability during endoscopy in subjects with a Mayo endoscopic subscore of 0 or 1 will confer an endoscopic subscore of 2.

## 3.3 Secondary Efficacy Endpoints

---

### Definitions of Efficacy Endpoints:

**Clinical Remission per Adapted Mayo Score:** stool frequency subscore (SFS)  $\leq 1$ , and not greater than baseline, rectal bleeding subscore (RBS) = 0, and endoscopic subscore  $\leq 1$

**Clinical Response per Adapted Mayo Score:** decrease from Baseline  $\geq 2$  points and  $\geq 30\%$ , PLUS a decrease in RBS  $\geq 1$  or an absolute RBS  $\leq 1$

**Clinical Response per Partial Adapted Mayo Score:** decrease from Baseline  $\geq 1$  points and  $\geq 30\%$ , PLUS a decrease in RBS  $\geq 1$  or an absolute RBS  $\leq 1$

**Clinical Remission per Full Mayo Score:** Full Mayo score  $\leq 2$  with no subscore  $> 1$

**Clinical Response per Full Mayo Score:** decrease from Baseline  $\geq 3$  points and  $\geq 30\%$ , PLUS a decrease in RBS  $\geq 1$  or an absolute RBS  $\leq 1$

**Endoscopic Improvement:** Mayo endoscopic subscore of 0 or 1

**Endoscopic Remission:** Mayo endoscopic subscore = 0

**Histologic Remission:** Geboes score of  $< 2.0$

**Mucosal Healing:** endoscopic and histologic remission

**Modified Baron Score:** The modified Baron score, which represents an endoscopic classification, ranges from 0 to 4, with 0 denoting normal mucosa, 1 granular mucosa with an abnormal vascular pattern, 2 friable mucosa, 3 microulceration with spontaneous bleeding, and 4 gross ulceration.

Note that evidence of friability during endoscopy in subjects with a Mayo endoscopic subscore of 0 or 1 will confer an endoscopic subscore of 2.

For this study, Baseline is defined as Week 0.

### Key Secondary Efficacy Endpoints for Induction Period (Weeks 0 to 12)

- Proportion of subjects with clinical remission per Adapted Mayo score at Week 8
- Proportion of subjects with clinical response per Adapted Mayo score at Week 8
- Proportion of subjects with clinical response per Partial Adapted Mayo score over time
- Proportion of subjects with clinical remission per Full Mayo score at Week 8 in subjects with a Full Mayo score of 6 to 12 at Baseline

- Proportion of subjects with Endoscopic remission at Week 8

### 3.4 Additional Efficacy Endpoints

---

- Change from Baseline in modified Baron score over time (at visits with endoscopy)
- Proportion of subjects with achievement of SFS = 0, RBS = 0, and Mayo endoscopic subscore = 0 over time (at visits with endoscopy)
- Time to clinical response per Partial Adapted Mayo score
- Proportion of subjects with endoscopic improvement over time (at visits with endoscopy)
- Proportion of subjects with clinical remission per Adapted Mayo score over time (at visits with endoscopy)
- Proportion of subjects with clinical response per Adapted Mayo score over time (at visits with endoscopy)
- Proportion of subjects with clinical response per Partial Adapted Mayo score over time
- Proportion of subjects with achievement of clinical remission per Adapted Mayo score over time among subjects who were taking corticosteroids at Baseline and subsequently discontinued corticosteroids for  $\geq$  90 days prior to the respective visit.
- Proportion of subjects with discontinuation of corticosteroid use for subjects taking corticosteroids at Baseline at all visits over time
- Proportion of subjects with endoscopic remission over time (at visits with endoscopy)
- Proportion of subjects with clinical remission per Full Mayo score over time in subjects with a Full Mayo score of 6 to 12 at Baseline (at visits with endoscopy)
- Proportion of subjects with clinical response per Full Mayo score over time in subjects with a Full Mayo score of 6 to 12 at Baseline (at visits with endoscopy)
- Proportion of subjects with SFS  $\leq$  1 over time
- Proportion of subjects with RBS = 0 over time
- Change from Baseline in RBS over time
- Change from Baseline in SFS over time
- Change from Baseline in fecal calprotectin (FCP) over time
- Change from Baseline in high sensitivity C-reactive protein (hs-CRP) over time
- Change from Baseline in Inflammatory Bowel Disease Questionnaire (IBDQ) over time
- Proportion of subjects with UC-related Hospitalizations (yes/no) over time
- Proportion of subjects with UC-related surgery (yes/no) over time
- Proportion of subjects reporting no bowel urgency over time
- Change from Baseline in weekly abdominal pain score over time

- Proportion of subjects with achievement of  $\geq 30\%$  reduction from Baseline in weekly abdominal pain score over time
- Proportion of subjects with weekly abdominal pain score = 0 over time
- Change from Baseline in number of extraintestinal manifestations (EIM) over time (as captured in the EIM electronic case report form [eCRF])
- Proportion of subjects with histologic remission over time (at visits with endoscopy)
- Proportion of subjects with mucosal healing (endoscopic and histologic remission) over time (at visits with endoscopy)
- Change from Baseline in Ulcerative Colitis Endoscopic Index of Severity (UCEIS) over time (at visits with endoscopy)
- Change from Baseline in UC-100 score over time (at visits with endoscopy)

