#### **Induction Period**

Up to approximately 40 subjects will be enrolled in the induction period to receive the following treatment:

- Ravaglimab 600 mg intravenous (IV) Week 0; ravaglimab 300 mg subcutaneous (SC) Weeks 2, 4, 6, 8, and 10.

Once the 30th subject completes Week 8 assessments an interim analysis will occur. This interim analysis will inform the planning of future Phase 2b and 3 studies. Enrollment into the induction period may continue until approximately 40 subjects have enrolled, or enrollment may be terminated if the study objectives are determined to have been met.

An endoscopy is required at Screening, and evaluation of endoscopic improvement will occur at Week 8. In order to explore the time-course of ravaglimab efficacy, subjects will continue through Week 12 and

will be assessed for clinical response per Partial Adapted Mayo score at Week 12. Subjects who complete the induction period and achieve clinical response per Partial Adapted Mayo score at Week 12 will be given the opportunity to continue into the maintenance period. Subjects not achieving clinical response per Partial Adapted Mayo score at Week 12 will be discontinued and have a follow-up visit (or call if a visit is not possible) 84 days from the last dose of study drug to obtain information on any new or ongoing AEs.

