#### **Maintenance Period**

Subjects who enter the maintenance period will receive OL ravagalisimab 300 mg SC every other week (eow) from Week 12 through Week 102.

[figure not shown]
[figure not shown]
At Weeks 52 and 104 subjects will undergo endoscopy. Clinical response and remission, as well as other exploratory endpoints will be evaluated throughout the study at specified time points. Patients who complete the maintenance period will have a follow-up visit (or call if a visit is not possible) 84 days from the last dose of study drug to obtain information on any new or ongoing AEs.

The schematic of the study is shown in [Figure 1](#). Further details regarding study procedures are located in the Operations Manual.

See Section [5.1](#) for information regarding eligibility criteria.

All video endoscopies and mandatory biopsies for histologic assessment will be centrally reviewed.

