## 5.4 Prior and Concomitant Therapy

---

Subjects taking oral aminosalicylates, immunomodulators, oral corticosteroids, and/or UC-related antibiotics at Baseline must continue their concomitant treatment for the duration of the induction period (through Week 12). Initiating and/or increasing doses of oral aminosalicylates, immunomodulators, oral corticosteroids, and/or UC-related antibiotics during the study is prohibited through Week 12. Decreasing doses of oral aminosalicylates, immunomodulators, oral corticosteroids, and/or UC-related antibiotics during the induction period is prohibited, except in the event of moderate-to-severe treatment related toxicities and after discussion with the AbbVie TA MD. Starting at Week 12 (maintenance period), oral aminosalicylates, immunomodulators, and/or UC-related antibiotics may be decreased or discontinued at the discretion of the Investigator. Starting at Week 12, initiating and/or increasing doses of oral aminosalicylates, immunomodulators, oral corticosteroids, and/or UC-related antibiotics is permissible after discussion with the AbbVie TA MD.

During the maintenance period, subjects can initiate an optional steroid taper at Week 12. While stopping the taper is permitted, increasing doses above the Baseline dose is permitted only after discussion with the AbbVie TA MD. Below is a suggested tapering schedule.

	Dose	Rate
Prednisone (or equivalent)	> 10 mg/day	5 mg/day per week
	≤ 10 mg/day	2.5 mg/day per week
Budesonide	≤ 9 mg/day	3 mg/day per week

Any questions regarding concomitant or prior therapy should be raised to the AbbVie emergency contact. Information regarding potential drug interactions with ravagalimab can be located in the ravagalimab Investigator's Brochure.

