## 5.5 Withdrawal of Subjects and Discontinuation of Study Drug or from Study Participation

---

A subject may voluntarily withdraw or be withdrawn from study participation, or be discontinued from study drug, at any time for reasons including, but not limited to, the following:

- Disease progression or lack of response to treatment.

- Clinically significant abnormal laboratory results or AEs, which rule out continuation of the study drug, as determined by the investigator or the AbbVie TA MD.
- The investigator believes it is in the best interest of the subject.
- The subject requests withdrawal from the study. This includes if a subject would like to discontinue after completion of the Week 52 visit.
- Eligibility criteria violation was noted after the subject started study drug and continuation of the study drug would place the subject at risk.
- Introduction of prohibited medications or dosages and continuation of the study drug would place the subject at risk.
- The subject becomes pregnant while on study drug.
- Subject has a malignancy, except for localized non-melanoma skin cancer. Discontinuation for carcinoma in situ of the cervix is at the discretion of the Investigator.
- Subject is significantly noncompliant with study procedures, which would put the subject at risk for continued participation in the trial.

Subjects who complete the induction period and do not achieve clinical response per Partial Adapted Mayo score at Week 12 will be discontinued.

For subjects to be considered lost to follow-up, reasonable attempts must be made to obtain information on the subject's final status. At a minimum, 2 telephone calls must be made and 1 certified letter must be sent and documented in the subject's source documentation.

AbbVie may terminate this study prematurely, either in its entirety or at any site. The investigator may also stop the study at his/her site if he/she has safety concerns. If AbbVie terminates the study for safety reasons, AbbVie will promptly notify the investigator.

During states of emergency or pandemic situations, it may be necessary to employ mitigation strategies to enable the investigator to ensure subject safety and continuity of care. Acceptable mitigation strategies are identified and included in the Operations Manual in [Appendix F](#).

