3.3 Additional Efficacy Endpoints

Additional efficacy endpoints are:

- Change from Baseline in modified Baron score over time (at visits with endoscopy)
- Achievement with stool frequency subscore (SFS) = 0, rectal bleeding subscore (RBS) = 0, and Mayo endoscopic subscore = 0 over time (at visits with endoscopy)
- Time to clinical response per Partial Adapted Mayo score
- Endoscopic improvement over time (at visits with endoscopy)
- Clinical remission per Adapted Mayo score over time (at visits with endoscopy)
- Clinical response per Adapted Mayo score at over time (at visits with endoscopy)
- Clinical remission per Partial Adapted Mayo score over time
- Clinical response per Partial Adapted Mayo score over time
- Clinical remission per Adapted Mayo score over time among subjects who were taking corticosteroids at Baseline and subsequently discontinued corticosteroids for \geq 90 days prior to the respective visit
- Discontinuation of corticosteroid use for subjects taking corticosteroids at Baseline at all visits over time
- Endoscopic remission over time (at visits with endoscopy)
- Clinical remission per Full Mayo score over time in subjects with a Full Mayo score of 6 to 12 at Baseline (at visits with endoscopy)
- Clinical response per Full Mayo score over time in subjects with a Full Mayo score of 6 to 12 at Baseline (at visits with endoscopy)

- Achievement of SFS ≤ 1 over time
- Achievement of RBS = 0 over time
- Change from Baseline in RBS over time
- Change from Baseline in SFS over time
- Change from Baseline in fecal calprotectin (FCP) over time
- Change from Baseline in high sensitivity C-reactive protein (hs-CRP) over time
- Change from Baseline in Inflammatory Bowel Disease Questionnaire (IBDQ) over time
- UC-related Hospitalizations (yes/no) over time
- UC-related surgeries (yes/no) over time
- No bowel urgency over time
- Change from Baseline in weekly abdominal pain score over time
- Achievement of $\geq 30\%$ reduction from Baseline in weekly abdominal pain score over time
- Achievement of Weekly abdominal pain score = 0 over time
- Change from Baseline in number of extraintestinal manifestations (EIM) over time (as captured in the EIM electronic case report form [eCRF])
- Histologic remission over time (at visits with endoscopy)
- Mucosal healing (endoscopic and histologic remission) over time (at visits with endoscopy)

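### The endpoint for remission after stopping corticosteroids counts only baseline users already off them for at least 90 days, so a post-baseline success sets its denominator

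*Protocol*

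**What the plan says.** Protocol 3.4 counts Adapted Mayo remission "among subjects who were taking corticosteroids at Baseline and subsequently discontinued corticosteroids for" at least 90 days before the respective visit. SAP 3.3 repeats it: "Clinical remission per Adapted Mayo score over time among subjects who were taking corticosteroids at Baseline and subsequently discontinued corticosteroids for" the same period. Neither document gives another denominator, and neither says that a baseline user still on steroids counts as a failure.

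The next endpoint in both lists is, in the protocol's words, "Proportion of subjects with discontinuation of corticosteroid use for subjects taking corticosteroids at Baseline at all visits over time". Its denominator is fixed at Baseline, but it requires neither remission nor 90 days off.

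Four other provisions decide who can enter the 90-day group:

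- Protocol 5.4 keeps baseline oral corticosteroids in place through Week 12, apart from dose decreases for certain toxicities. Then: "During the maintenance period, subjects can initiate an optional steroid taper at Week 12". Starting or increasing steroids after Week 12 is allowed after discussion with the sponsor's medical director.
- Protocol 5.5: "Subjects who complete the induction period and do not achieve clinical response per Partial Adapted Mayo score at Week 12 will be discontinued".
- Protocol 4.1, Maintenance Period: "At Weeks 52 and 104 subjects will undergo endoscopy".
- SAP 8.5 analyses binary maintenance endpoints as observed. Under SAP 8.2 a subject without an evaluation at a visit is left out of that visit.

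**The concern.** Ninety days off steroids is something a subject achieves after Baseline, and it is part of what a reader would call success on this endpoint. Once it sits in the denominator, a baseline user who does badly is removed and not counted as a failure. The other subset endpoints in Protocol 3.4 condition on a baseline feature: a Full Mayo score of 6 to 12, or steroid use at Baseline. This is the only one that conditions on a later outcome.

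At stake is how one number in the report is read. A percentage with this label is easily taken as the share of steroid-treated patients who reached remission off steroids. It is the share in remission among those who had already come off, which in a trial of about 40 subjects may be a handful of people.

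**Working it through.** The documents state no rate, power or sample size for this endpoint, so there is no planned figure to reproduce. The check concerns denominators and timing.

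**Denominators.** Let M be the number of FAS subjects on corticosteroids at Baseline, m the number of these off for at least 90 days at the visit, and x the number both off and in remission. Then x ≤ m ≤ M.

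- Rate as written: x/m.
- Rate over all baseline users: x/M.
- Ratio when x > 0: (x/m)/(x/M) = M/m, which is at least 1 and exceeds 1 whenever m < M.

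The direction is therefore settled without data. The size depends only on M/m; the share in remission cancels.

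**Size, under assumed counts.** M and m are not in the documents. The assumptions are 12 to 20 baseline users out of 40, 30% to 70% of them off for at least 90 days, and 30% to 50% of those in remission. Examples across that range:

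| M | m | x | As written, x/m | All baseline users, x/M | M/m |
|---|---|---|---|---|---|
| 20 | 14 | 7 | 50% | 35% | 1.43 |
| 16 | 8 | 4 | 50% | 25% | 2.00 |
| 20 | 6 | 3 | 50% | 15% | 3.33 |

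The same 50% goes with 35%, 25% or 15% of baseline users, which is what the reported figure hides. Over the whole assumed range M/m runs from about 1.4 to 3.3.

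**What shrinks m.** Week 12 non-responders leave the study. The taper is optional, so some responders may never start it. A subject who restarts steroids is no longer 90 days off and leaves the denominator; SAP 8.1 treats steroid use as non-response only through the end of induction, so no maintenance rule counts a restart as failure. The as-observed rule also drops subjects with no evaluation.

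**Timing.** Week 8 is Day 57, which is 56 days after Baseline, or 63 with the 7-day window. Both are below 90, so no subject qualifies at Week 8 even if steroids stopped on Day 1. Week 12 has no endoscopy and hence no Adapted Mayo score. For steroids held through Week 12, 90 days off is reached at:

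- stopped at Week 12: 12 + 90/7 = Week 24.9;
- budesonide 9 mg/day, suggested taper of 3 weeks: 12 + 3 + 90/7 = Week 27.9;
- prednisone 20 mg/day, suggested taper of 2 + 4 = 6 weeks: 12 + 6 + 90/7 = Week 30.9.

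In each case the next scheduled endoscopy is Week 52. The scheduled visits that can contribute are Weeks 52 and 104. Premature discontinuation visits in maintenance also include endoscopy, so an unscheduled score is possible.

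**The case against.** The strongest reply is that a conditional proportion is a legitimate description. The stated objective is only to explore efficacy, safety and tolerability, and nothing in either document says that this endpoint is meant to measure steroid sparing. The companion endpoint would show a low discontinuation rate beside it, and Adapted Mayo remission without the steroid condition is listed too. The endpoint is one of about 30 additional ones, it is summarised descriptively, and no stated decision depends on it.

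Most of this stands. The conditional rate is valid if labelled as conditional, and it is too high only relative to a different target, remission off steroids among all baseline users. The companion endpoint gives real context. It does not give the joint rate, because it requires neither remission nor 90 days off, and no other listed endpoint supplies that rate.

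Two further points against change also stand. Loss of Week 12 non-responders affects every maintenance endpoint, not this one alone. And because the taper is optional, a full denominator counts a subject in remission who chose not to taper as not achieving the endpoint. With no control arm, neither form isolates a steroid-sparing effect.

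A reader might go further and infer that the plan overstates ravagalimab's effect about threefold, or that the trial's main results are affected. The documents support neither. They give no counts, and a ratio near 3 sits at the upper end of an assumed range. The primary and key secondary endpoints are all assessed by Week 12, before this endpoint can be populated. A reader might also take Week 31 as the earliest feasible time. It is only the case of prednisone at the highest permitted entry dose on the suggested schedule.

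**Conclusion.** The point holds as a defect in the definition of one additional, descriptive endpoint. On the plain wording of both documents, sustained steroid withdrawal sets the denominator. The reported rate is therefore at least as high as the rate of remission off steroids among all baseline users, and strictly higher whenever any baseline user is not 90 days off and at least one remission occurs. That conclusion needs no assumption. The size does: about 1.4 to 3.3 times, if 30% to 70% of 12 to 20 baseline users are off for at least 90 days. Week 8 cannot contribute. Primary and key secondary results are untouched. The change is worth making because it is cheap and would alter the reported figure.

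**What to change.** - **Protocol 3.4 and SAP 3.3:** define the endpoint as the proportion of all FAS subjects taking corticosteroids at Baseline who, at Week 52 or Week 104, are in Adapted Mayo remission and have been off corticosteroids for at least 90 days. Subjects still on steroids, restarted, discontinued or missing count as not achieving it.
- **SAP 8.5:** state that this endpoint uses non-responder handling in place of the as-observed rule for maintenance. Without that sentence the new definition would conflict with the SAP.
- **Supplement:** keep the conditional rate if wanted, labelled as conditional and shown with its numerator and denominator.

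The cost is revised wording in two places, one exception in the SAP and one table definition. Concomitant therapy and Adapted Mayo scores are already collected at these visits, and patient management does not change. The reported rate will be lower, and subjects in remission who chose not to taper will count as not achieving the endpoint; a footnote giving their number would make that visible.
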